11.15 Trial day

Trial day will be calculated from the reference start date, and will be used to show start/end day of assessments and events. Reference start date is defined as the day of the first IMP administration in period 1. Trial Day 1 is the day of first IMP administration in period 1. The day before is defined as Trial Day -1 (no Trial Day 0 is defined). Trial day will be calculated accordingly:

- If the date of the event is on or after the reference start date then:

Trial day = (date of event – reference start date) + 1.

- If the date of the event is prior to the reference start date then:
Trial day = (date of event – reference start date).

12 Trial Subjects

This section includes specifications for reporting subject disposition and treatment/trial discontinuations. Additionally, procedures for reporting protocol deviations are provided.

12.1 Disposition of Subjects and Discontinuations

All subjects who provide informed consent will be accounted into this study. Subject disposition and withdrawals will be presented for the Screening Population.

The following summaries will be produced by treatment sequence and overall for each food consumption condition group:

- Total number of subjects screened (i.e. subjects who gave informed consent)
- Number of subjects screening failures, grouped by the primary reason for study exclusion
- Numbers of randomized subjects
- Number of subjects treated in each period
- Number of subjects who complete the trial
- Number of subjects who discontinued the study treatment after administration, grouped by the main reason
- Number of subjects who terminated the study prematurely, grouped by the main reason
- Number of subjects included in Safety Population
- Number of subjects included in PK Population

Corresponding individual listings will be prepared (sorted by group, treatment sequence and subject).

Additionally, a listing of the screening failures will be produced with the reason of non-inclusion in the treatment phase.

Listings with visit dates will also be carried out by group, treatment sequence and subject.

12.2 Protocol Deviations

12.2.1 Important Protocol Deviations

Important protocol deviations will be based on the Clinical Trial Management System (CTMS) data and determined by medical review process. All important protocol deviations will be included in SDTM datasets, if identified through medical review. The Analysis Data Model (ADaM) datasets will be derived from SDTM and include all important protocol deviations.

A data review meeting will be held to discuss and update the definition of important protocol deviations, so as to determine the evaluability of the subjects prior to database lock.

The following outputs will be provided by treatment sequence and overall, for each food consumption condition group:

- Summary of important protocol deviations relating to inclusion/exclusion criteria
- Summary of other important protocol deviations post inclusion criteria

All important protocol deviations will be listed. A listing presenting protocol deviations relating to inclusion/exclusion criteria and a listing presenting other deviations will be produced.

13 Demographics and Other Baseline Characteristics

Unless otherwise specified, demographic data and other baseline characteristics will be presented for the Safety Population.

Summaries of the key demographics overall and by treatment sequence for each group are to be provided. Continuous variables will be summarized using the descriptive statistics. Quantitative variables will be summarized by counts and percentages. No statistical testing will be carried out for demographic or other baseline characteristics.

13.1 Demographics

Demographic characteristics will be summarized using the following information from the Screening/Baseline Visit eCRF pages.

Demographic characteristics

- Age (years): summary statistics
Age (years) = (date of informed consent - date of birth + 1) / 365.25
- Sex: Male, Female
- Race: Asian
- Weight (kg): summary statistics
- Height (cm): summary statistics

- BMI (kg/m²): summary statistics

13.2 Medical History

The medical history will be summarized from the “Medical History” eCRF page, using MedDRA, Version 21.0 or higher version, preferred term (PT) as event category and MedDRA system organ class (SOC) body term as Body System category.

Medical history will be displayed in terms of frequency tables: ordered by primary SOC and PT in alphabetical order.

13.3 Other Baseline Characteristics

The following baseline characteristics will be reported overall and by treatment sequence for each food consumption group:

- Nicotine and Alcohol Consumption
- Serology: HAV antibody, HBsAg, HCV antibody, HIV antibody, TP antibody

Baseline characteristics with respect to vital signs, ECG recordings and laboratory tests will be part of Section 17 (Safety Evaluation).

Results of chest x-ray and serum pregnancy test (for women of childbearing potential) will be presented only in the listings.

13.4 Urine drug abuse test and breath test of alcohol

Urine screening of drug and breath test of alcohol will be overall and by treatment sequence and visit for each food consumption group.

14 Previous or Concomitant Medications/Procedures

Previous and concomitant medication/ procedure will be tabulated for Safety Population. All medications and procedures will be presented in the listings.

Medications will be coded using World Health Organization Drug Dictionary Enhanced (WHO-DDE) Version March 1, 2018 or higher version. Procedures will be coded using MedDRA Version 21.0 or higher version.

Previous medications are medications started and ended before first IMP administration.

Concomitant medications/ procedures are medications/ procedures, other than trial medications/ procedures, which are taken by subjects any time on-trial (include medications/ procedures which started before the first IMP administration and were ongoing after first IMP administration, or started on or after the first IMP administration day).

Previous and concomitant medications will be summarized overall for both food consumption groups as well as overall and by treatment sequence for each food consumption group, and by PT

and ATC 2nd level, respectively. The listing of previous and concomitant medications/procedures will be generated.

The listing of previous and concomitant procedures will be generated.

Missing or partial dates for medication/ procedure will not be imputed. In the case where it is not possible to define a medication/ procedure as previous or concomitant, the medication/ procedure will be classified by the worst case; i.e. considered as both previous and concomitant.

15 Treatment Compliance and Exposure

Population: Safety Population

Safety Population will be used to list the IMP administration. IMP administration will be listed by group, treatment sequence and subject with treatment, date and time of administration.

Missing or partial dates or time for IMP administration will not be imputed.

The food intake information will be listed by subject, treatment sequence for each group at Day 1 and Day 8.

16 Endpoint Evaluation

16.1 Primary Endpoint Analyses

The primary endpoints are the following PK parameters calculated from metformin plasma concentrations under fasting or fed condition:

C_{\max} of metformin

$AUC_{0 \rightarrow t}$ of metformin

The null and alternative hypotheses are the following:

$H_0 : \text{for } AUC_{0 \rightarrow t} \ \mu_T / \mu_C \leq 0.8 \text{ or } \mu_T / \mu_C \geq 1.25$, for at least 1 primary endpoint
 $\text{for } C_{\max} \ \mu_T / \mu_C \leq 0.8 \text{ or } \mu_T / \mu_C \geq 1.25$

$H_1 : \text{for } AUC_{0 \rightarrow t} \ 0.8 < \mu_T / \mu_C < 1.25$, for both primary endpoints and for both fasting and
 $\text{for } C_{\max} \ 0.8 < \mu_T / \mu_C < 1.25$
fed groups

where μ_T and μ_C are the means of primary endpoints following test IMP and reference IMP (Treatment A and Treatment B), respectively.

The analysis of primary endpoints will be based on PK Population.

The primary endpoints, C_{max} and $AUC_{0 \rightarrow t}$ in fasting and fed group, will be log-transformed and a mixed-effects model will be applied. The model will include fixed effects for sequence, treatment, and period and a random effect of subject nested within sequence. Treatment differences on the log scale will be estimated for the parameters together with their 90% CIs. The least squares mean together with their 95% CIs by treatment will also be estimated. Point estimates and CIs will be back-transformed to the original scale for presentation, i.e., ratios of geometric means and corresponding 90% CIs for Treatment A/Treatment B, and geometric means and corresponding 95% CIs by treatment, respectively. Intra-subject CV estimated from the model will also be presented. Bioequivalence will be assessed separately in the fed and in the fasted group, and the trial will be considered successful only if BE is established for both primary parameters in both groups. The BE will be considered established if the 90% CIs for the ratios of geometric means between the investigational product and the comparator fall within 80.00% to 125.00% for all these comparisons.

The following example code could be used:

```
proc mixed data=pkparam;
  by foodconsumption param;
  class sequence period trt subjid;
  model lnest = sequence period trt /ddf=kr;
  random subjid(sequence);
  estimate 'A vs B' trt 1 -1 /alpha=0.1 cl;
  lsmeans trt /alpha=0.05 cl;

run;
```

All primary PK endpoints will be descriptively summarized as described in [Section 16.3.2](#). Graphs of individual values and geometric mean will be presented for primary PK parameters versus treatment and food consumption condition. Boxplots will also be created for primary PK parameters versus treatment for the fed and the fasted conditions.

16.2 Secondary Endpoint Analyses

All secondary PK endpoints will be descriptively summarized as described in [Section 11](#). The secondary PK endpoints are the following parameters in plasma for metformin:

t_{max} , $t_{1/2}$, λ_Z , $AUC_{0 \rightarrow \infty}$, $AUC_{extra\%}$, $CL_{f/f}$, $V_{Z/f}$.

For t_{max} , the Hodges-Lehmann estimates for the treatment differences and corresponding 90% CIs according to the Tukey method will be calculated.

The mixed-effects model for treatment comparison as described for the primary endpoints will also be applied to $AUC_{0 \rightarrow \infty}$. The ratios of geometric means and corresponding 90% CIs for Treatment A/Treatment B will be estimated separately for fed and fasted treatments. Graphs of individual $AUC_{0 \rightarrow \infty}$ values and geometric mean will be presented by treatment and food consumption condition.

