9.4.3 Analysis of Secondary Endpoints

The secondary PK endpoints are the following parameters in plasma for metformin:

- t_{\max} , $t_{1/2}$, λ_Z , $AUC_{0-\infty}$, $AUC_{\%extra}$, CL/f , V_z/f .

For t_{\max} , the Hodges-Lehmann estimates [20] for the pairwise treatment differences and the corresponding 90% CIs according to the Tukey method will be calculated.

The mixed model as described above will also be applied to $AUC_{0-\infty}$. A 90% CI will be calculated for the ratios of geometric means of the test IMP and reference IMP.

All secondary endpoints will be summarized descriptively by group and treatment in the PK Population.

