7.2 Randomization

Each eligible participant will be allocated to a treatment sequence according to a computer-generated randomization schedule. Subjects will be identified only by their assigned participant number. The participants will receive consecutive participant numbers in the order of their enrollment into the study.

A total of 54 eligible healthy male and female Chinese participants (38 in fasting group and 16 in fed group, Table) who meet the eligibility criteria will be randomized (with each gender representing no less than 1/4 of the total number within each group, i.e., no less than 10 participants

of each gender in the fasting group and no less than 4 in the fed group) on Day 1, in a 1:1 ratio to 1 of 2 treatment sequences: Sequence A-B or Sequence B-A as presented in Table .

Sequence A to B:

- Day 1 (Period 1), Treatment A: the administration of a single dose of test GXR
- Day 8 (Period 2), Treatment B: the administration of a single dose of reference GXR

Sequence B to A:

- Day 1 (Period 1), Treatment B: the administration of a single dose of reference GXR
- Day 8 (Period 2), Treatment A: the administration of a single dose of test GXR

The 2 doses will be separated by a Washout period of approximately 7 days ([Table 7](#)).

Table 5 Randomization Allocation

	Day 1	Day 8
Fasting group (n= 38)	Treatment A (n= 19)	Treatment B (n= 19)
	Treatment B (n= 19)	Treatment A (n= 19)
Fed group (n= 16)	Treatment A (n= 8)	Treatment B (n= 8)
	Treatment B (n= 8)	Treatment A (n= 8)

Table 6 Assignment to Administration Sequences

	Day 1	Day 8
Sequence A to B	GXR 500 mg (Merck Nantong manufactured) (Test Product)	GXR 500 mg (Merck Darmstadt manufactured) (Reference Product)
Sequence B to A	GXR 500 mg (Merck Darmstadt manufactured) (Reference Product)	GXR 500 mg (Merck Nantong manufactured) (Test Product)

GXR=Glucophage® Extended Release.

Table 7 Instruction of Study Periods

Screening Period	Randomization	Treatment Period 1	Washout Period	Treatment Period 2	End-of-Study Discharge	Conditional Follow-up

Day -14 to Day -1	Day -1	Day 1 to Day 3 Inpatient	7 days Inpatient	Day 8 to Day 10 Inpatient	Day 10	Day 15
----------------------	--------	-----------------------------	---------------------	------------------------------	--------	--------

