This 2 x 2 crossover design for comparison of 2 treatments complies with the Chinese guideline for BE studies [2]. The guideline recommends 2 sequences in order to minimize the effect of individual and periodic differences. The guideline suggests that the duration of a Washout Period should be at least 7 times $t_{1/2}$. Therefore, 7 days have been assigned as the Washout Period duration to assure that the main collection times in Period 2 can occur on a weekday.

Participants will only be replaced if the number of participants within each group falls below 28 (fasting) or 12 (fed). The participant who is replacing a discontinued participant will then be allocated to the treatment sequence of the participant who discontinued.

8 Overview of Planned Analyses

The methods described in this document will be applied to the preparation of tables, figures and listings (TLFs). Statistical analyses will be performed using cleaned electronic case report form (eCRF) data collected.

This SAP will cover the final analysis only. The final analysis will be performed only after the last subject has completed the study with all study data in-house and all data queries resolved. The SAP will be finalized prior to database lock.

9 Changes to the Planned Analyses in the Clinical Trial Protocol

There are no changes to the planned analyses.

10 Protocol Deviations and Analysis Sets

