16.3.2 Estimation of Individual Pharmacokinetic Parameters by Noncompartmental Analysis

For the PK analysis, predose sample concentrations that are below the LLOQ or that are missing will be assigned a numerical value of zero for the calculation of AUC. Any anomalous concentration values observed at predose will be identified in the CSR, and if the anomalous predose concentration value is greater than 5.00% of the C_{max} in the profile, the profile will be included in the PK analysis, but the concentration data and the corresponding derived PK parameters will be excluded from summaries and inferential statistics as appropriate; handling of the data will be documented in the CSR.

Pharmacokinetic parameters will be calculated using standard noncompartmental methods (calculation method: linear up log down) and the actual administered dose. Pharmacokinetic parameters will be calculated and listed for all volunteers who provide sufficient concentration-time data. At least 3 valid, postdose concentration points will be required in the PK profile to obtain any PK parameter estimate.

Pharmacokinetic parameters will be calculated using the actual elapsed time since dosing, given with a precision of 14 significant digits or the SAS format Best12. In cases where the actual sampling time is missing, calculations will be performed using the scheduled time. Otherwise, there will be no further imputation of missing data other than for a missing predose concentration as stated above.

For each subject in the PK Population the following PK parameters will be calculated for metformin, where appropriate:

Symbol	Definition
AUC _{0→t}	The AUC from time zero (= dosing time) to the time the last concentration is at or above the LLOQ (t _{last}). Calculated using the mixed log linear trapezoidal rule (linear up, log down). Units: ng*h/mL.
AUC _{0→∞}	The AUC from time zero (= dosing time) extrapolated to infinity, based on the predicted value for the concentration at t _{last} , as estimated using the linear regression from λ _z determination. AUC _{0→∞} = AUC _{0→t} + C _{last pred} / λ _z . Units: ng*h/mL. The predicted AUC _{0→∞} will be reported.
AUC _{extra%}	The AUC from time t _{last} extrapolated to infinity given as percentage of AUC _{0→∞} . AUC _{extra%} = (extrapolated area/AUC _{0→∞}) *100. The predicted AUC _{0→∞} will be used. Units: %.

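### Does the tmax comparison need a stated Hodges-Lehmann form with a period adjustment?

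*SAP*

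**What the plan says.** Protocol 9.4.3 plans Hodges-Lehmann estimates for tmax "for the pairwise treatment differences and the corresponding 90% CIs according to the Tukey method will be calculated". SAP 16.2 repeats the plan without the word *pairwise*: "the Hodges-Lehmann estimates for the treatment differences and corresponding 90% CIs according to the Tukey method will be calculated". Neither names the unit of analysis or mentions period or sequence. The only code in the SAP (16.1) is for the log-transformed parameters.

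For Cmax and AUC0-t, SAP 16.1 states: "The model will include fixed effects for sequence, treatment, and period and a random effect of subject nested within sequence". For AUC0-inf, SAP 16.2 adds: "The mixed-effects model for treatment comparison as described for the primary endpoints will also be applied to" that parameter.

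Three other places bear on the point:

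- SAP 7.2 randomizes participants "in a 1:1 ratio to 1 of 2 treatment sequences: Sequence A-B or Sequence B-A", giving 19:19 (fasting) and 8:8 (fed). Replacement starts only once a group falls below 28 (fasting) or 12 (fed), and then "The participant who is replacing a discontinued participant will then be allocated to the treatment sequence of the participant who discontinued".
- SAP 16.3.2: "Pharmacokinetic parameters will be calculated using the actual elapsed time since dosing". tmax values are therefore not all tied at nominal times.
- SAP section 9 declares no departure from the protocol's planned analyses.

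**The concern.** Three analyses could carry the Hodges-Lehmann name here:

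- the paired form, using Walsh averages of each participant's test-minus-reference difference;
- a two-sample form comparing half period differences between sequences, which removes a period effect;
- a two-sample form that treats test and reference values as independent.

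They give different intervals, and the text does not name one. If the paired form is meant, tmax is the only formally compared parameter with no allowance for period. A period shift then inflates the spread of the paired differences. If losses leave the sequences unequal, it also biases the estimate. At stake is the reported tmax difference and its 90% interval, which serve the secondary objective of comparing additional PK parameters.

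**Working it through.** **Which form.** Each participant receives both products, and there are only two. Reading *pairwise* as 'for every pair of treatments' adds little, because there is one pair. Within-participant differences with signed-rank (Tukey) limits are the natural reading. Since SAP section 9 declares no changes, dropping the word in SAP 16.2 does not open another option.

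**Algebra for the paired form.** Let δ be the test-minus-reference difference, D the Period 2 minus Period 1 shift, σ the within-participant SD, n1 the number in A-B and n2 the number in B-A.

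- A-B participants have expected difference δ − D; B-A participants have δ + D.
- Average: δ − D(n1 − n2)/(n1 + n2). With n1 = n2 the shift cancels.
- At equal sequences the variance of a difference is 2σ² + D², against 2σ² once period is removed. The width ratio is about √(1 + D²/2σ²). With σ = 1 h this is √1.5 = 1.22 at D = 1 h and √1.125 = 1.06 at D = 0.5 h.

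**Simulation.** The documents give neither D nor any tmax SD, and they state no tmax figure to reproduce. Assumed: mean tmax 5 h, within- and between-participant SD 1 h, no true difference, the protocol's sampling grid, and actual times inside the ±2 min window (±5 min from 24 h).

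*Equal sequences, paired against adjusted interval:* at D = 0.5 h the paired interval is 1% (8:8) and 4% (19:19) wider. At D = 1 h it is 18% and 21% wider, with coverage about 96% against 91–92%. The excess is smaller at 8:8 partly because the exact adjusted interval has a higher attained level there (91.7% against 90.7%). The result depends on σ: for SD from 0.5 to 1.5 h, the excess at D = 1 h runs from 64% down to 6% (8:8) and from 83% down to 10% (19:19).

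*Accuracy of the estimate (RMSE) at D = 1 h, paired against adjusted:* 0.395 and 0.397 h at 8:8; 0.262 and 0.270 h at 19:19; 0.412 and 0.409 h at 8:7; 0.269 and 0.273 h at 19:18. There is no meaningful difference.

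*Unequal sequences at D = 1 h:*

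| Split | Formula bias (h) | Simulated bias (h) | Paired coverage |
|---|---|---|---|
| 15:13 | −2/28 = −0.07 | −0.08 | 95% |
| 7:5 | −2/12 = −0.17 | −0.18 | 94% |
| 17:11 | −6/28 = −0.21 | −0.22 | 89% |
| 8:4 | −4/12 = −0.33 | −0.36 | 89% |

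These are splits at the replacement floor, meaning 4 of 16 or 10 of 38 participants lost. Even then, with losses at random, 8:4 has probability 2 × C(8,4)/C(16,4) = 140/1820 = 8%, and 17:11 or worse has 6%. With one loss (8:7 or 19:18) the bias is −0.07 or −0.02 h.

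*Change in interval width if the adjusted form replaced the paired form:*

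| Split | D = 0 | D = 0.25 h | D = 0.5 h | D = 1 h |
|---|---|---|---|---|
| 19:19 | +1 to 2% | 0% | −4% | −18% |
| 8:8 | +5% | +3% | −1% | −15% |
| 7:5 | +10% | +8% | +3% | −11% |
| 8:4 | +17% | +16% | +12% | −3% |

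**Is a shift near 1 h likely?** One hour is a full sampling step between 1 and 8 h. The documents give no reason to expect it. Participants stay in the unit from Day −1 to Day 10 (Protocol Table 1, note a). The fasting, breakfast, fluid and sampling rules are the same in both periods (Protocol 6.1.2, 6.8.3 and Table 6).

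**The case for a change.** The best case for a change is that a SAP should fix the estimator before data are seen, and that one sentence would do it. Even without a period effect, the independent-samples form gives wider intervals than the paired form: 1.77 against 1.31 h at 8:8 (35%) and 1.17 against 0.80 h at 19:19 (46%). tmax is also, besides Cmax, the only rate-related measure with a formal treatment comparison, which matters for an extended-release tablet. In the extreme fasting split of 19:9 with a 1 h shift, paired coverage falls to about 76%.

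It stands that the wording is terse and that the paired form assumes no period effect. The 35–46% gap, however, requires an analyst to ignore the pairing in a crossover, against the protocol's own word. The 19:9 split needs all ten losses in one sequence, which at random has probability 2 × C(19,10)/C(38,10), about 0.04%. A rank-based location estimate is a different method from the mixed model, so the lack of matching terms is no contradiction; nothing in the plan promises a period-adjusted tmax.

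**Conclusion.** No change is needed. The unstated form is a gap that the protocol's wording and the design let an analyst fill with the paired estimate. Preferring a period-adjusted estimate is a trade-off without a clear winner. It costs interval width in the small fed group when there is no shift and gains nothing at 0.25 h. It helps materially only for a shift near 1 h, which the documents do not suggest. At equal sequences the paired estimate is unbiased and its interval, if anything, too wide. Appreciable bias (about 0.2 to 0.4 h) needs both a 1 h shift and a heavily depleted, uneven group. Success depends only on Cmax and AUC0-t, so no bioequivalence conclusion can move.

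The sizes rest on an assumed SD of 1 h and assumed shifts of 0 to 1 h. A smaller within-participant SD would make the paired interval more conservative at a 1 h shift, without biasing the estimate when sequences are equal.
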